### 5.2.4 Early Terminations Assessments

Early termination assessments will be mapped to closest scheduled visit using the analysis windows described in Table 3. If the planned visit that an early termination assessment is mapped to has occurred and data was collected, then the early termination assessment will not be included in the statistical analyses or summaries of any endpoint but will only be included in the listing, otherwise if the planned visit hasn't occurred or it has occurred but not all applicable assessments were completed, then assessments from the early termination visit mapped to that visit will be used in the statistical analyses and summaries.

**Table 3.** Analysis Windows

Visit	Window Start Day	Window End Day
Day 8	Day 2	Day 11
Day 15	Day 12	Day 18
Day 21	Day 19	Day 24

Day 28

Day 25

Day 30

For sensitivity analyses of the primary endpoint purposes, should an early termination assessment occur that is mapped to a window where a planned visit was collected and where the PANSS score was correctly completed, the PANSS score collected at the early termination assessment will be used to replace the primary endpoint value at the planned visit.

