#### **5.2.17 Unscheduled Visits**

Only values collected at scheduled assessments values will be tabulated, unless otherwise stated. All repeat/unscheduled assessments will be included in all listings in the relevant appendices to the Clinical Study Report (CSR).

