### 5.13.2 Laboratory Data

Descriptive statistics of the observed values and change from baseline (continuous data) will be presented by treatment group and visit for each hematology, urinalysis, chemistry, coagulation, and hormone (ACTH, TSH, cortisol) parameter. Each measurement (continuous data) will be classed as below, within, or above normal range, based on ranges supplied by the laboratory used. Shift tables in relation to the normal range from baseline to each follow-up visit will be presented.

A summary of the number of abnormal parameter values will also be provided. All laboratory data will be listed, with a separate listing only including abnormal (i.e. out of range) values.

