#### **5.13.5    Physical Examination**

The body systems within the physical examination data throughout the study will be summarized by treatment (Normal, Abnormal NCS, Abnormal CS). A shift table will be also presented, with shift from baseline to each post-baseline visit.

All PE data will also be listed.

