#### **5.13.7    C-SSRS**

Suicidal ideation and suicidal behavior as measured by the C-SSRS will be summarized using frequencies and percentages by treatment group and timepoint. All C-SSRS data will also be listed.

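### Safety values measured at an early-termination visit are left out of the by-visit summaries when the window already holds a completed planned visit, and no last post-baseline row restores them

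*SAP*

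**What the plan says.** SAP 5.2.4 assigns ET assessments to four windows (Table 3): Day 8 covers Days 2–11, Day 15 covers Days 12–18, Day 21 covers Days 19–24 and Day 28 covers Days 25–30. Where the planned visit took place and yielded data, "the early termination assessment will not be included in the statistical analyses or summaries of any endpoint but will only be included" in the listing. The ET value is used if the planned visit did not take place, or if "it has occurred but not all applicable assessments were completed". SAP 2.2.4 lists laboratory tests, vital signs, ECG, the SAS, AIMS and BARS, the C-SSRS and physical examination as safety endpoints, so a rule for any endpoint covers them.

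The one stated exception concerns efficacy. For sensitivity analyses of the primary endpoint, "the PANSS score collected at the early termination assessment will be used to replace the primary endpoint value at the planned visit".

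The safety displays are organised by visit. For laboratory data (5.13.2), "Shift tables in relation to the normal range from baseline to each follow-up visit will be presented". Vital signs (5.13.3) and ECG (5.13.4) are summarised by visit or follow-up. C-SSRS results (5.13.7) "will be summarized using frequencies and percentages by treatment group and timepoint". The three extrapyramidal scales (5.13.8–5.13.10) get observed and change values, which Protocol 10.4.5.7 asks for by visit. No safety section and no title in the table list has a last or worst post-baseline row. The worst-case rule for ECG (5.2.10) works across the triplicate readings at one time point, not across visits.

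**The concern.** Protocol 7.2.14 asks sites to collect vital signs, ECG, laboratory tests, C-SSRS and the three extrapyramidal scales at an ET visit. For a patient who leaves shortly after a planned visit, the rule sets these measurements aside in favour of older ones. The tables then describe the patient as of the last planned visit rather than at withdrawal. The plan recognises that a withdrawal value can matter, since it makes room for one on PANSS, but gives safety no equivalent.

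The rule is also unclear in its unit. Its first branch turns on whether the planned visit yielded data, and its second on whether all applicable assessments were done. The choice matters for TSH, coagulation, and ACTH and cortisol, which the Schedule of Assessments places after baseline only at Day 28 or ET. Two programmers could produce different tables from the same data.

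**Working it through.** The plan gives no figure for this point, and the number randomised is blacked out, so sizes are shares of patients.

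**Inputs.** Windows: SAP Table 3. Visit tolerance of ±1 day at Days 8, 15 and 21: Protocol 7.1. Drop-out of 25%: SAP 3. Possible ET days: Days 2 to 27, which is 26 days. An ET day is displaced if it falls later than the completed planned visit in the same window.

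**Count.** Share of randomised patients = 25% × displaced days / 26, assuming evenly spread exits and an ET visit for every drop-out.

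| Planned visits held | Displaced ET days | Of 26 | Age of value kept | Share of patients |
|---|---|---|---|---|
| One day early (7, 14, 20) | 8–11, 15–18, 21–24 | 12 (46.2%) | 1–4 days | 11.5% |
| Nominal (8, 15, 21) | 9–11, 16–18, 22–24 | 9 (34.6%) | 1–3 days, mean 2.0 | 8.7% |
| One day late (9, 16, 22) | 10–11, 17–18, 23–24 | 6 (23.1%) | 1–2 days | 5.8% |

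Divided over the Day 8, 15 and 21 rows, that is 8.65% / 3 = 2.9% per row (1.9% to 3.8%).

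**Other exit patterns, nominal visit days.**
- Exits falling linearly (weight 27 − day): 93 / 325 = 28.6%; × 25% = 7.2%.
- Exits rising linearly (weight day − 2): 132 / 325 = 40.6%; × 25% = 10.2%.
- Even exits, half of drop-outs attending an ET visit: 8.65% / 2 = 4.3%.

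**Tables.** Vital signs, BMI and waist, and orthostatic hypotension (14.3.6.1–3) make 3. Hematology, chemistry and urinalysis with their shifts (14.3.7.1–5) make 5. ECG (14.3.7.8–9) makes 2, and the extrapyramidal scales (14.3.7.11–13) make 3. The total is 13, plus the by-timepoint C-SSRS table (14.3.7.10).

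**Tests scheduled after baseline only at Day 28 or ET.** Within Days 2–27 the windows hold 10, 7, 6 and 3 days. So 10 + 7 + 6 = 23 of 26 ET days map to Day 8, 15 or 21 (25% × 23 / 26 = 22.1% of patients), and 3 map to Day 28 (2.9%).
- Read per visit: with visits on nominal days, 9 of the 23 are dropped, and these are the patient's only post-baseline values. The other 14 are filed under a visit where the test is not scheduled.
- Read per assessment: all 23 are kept, but filed under such a visit.

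**The case against.** The strongest reply is that little is lost. These are descriptive tables with no hypothesis test. Most tests retain a value about two days older, and only about 2.9% of patients are affected in any one row. Protocol 10.4.5.3–10.4.5.7 asks for summaries by time point and shift tables, which the SAP provides; it does not ask for a last or worst row. All of that stands, and it sets the level of the point.

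A reader might infer that a safety signal at withdrawal disappears from the report. The documents do not support that. Protocol 8.2.1 and 8.2.2 require an AE form for clinically noteworthy changes in physical examination and vital signs. Sections 9.1.4 and 9.2.1 bring in laboratory and ECG findings that are symptomatic, need treatment, lead to discontinuation or are judged significant. AE tables are not windowed. The SAP also plans a separate listing of abnormal laboratory values, a flag for orthostatic hypotension and a listing of ECG abnormalities. What remains uncovered is the measured size of the change, and any change that meets none of these criteria, such as an asymptomatic shift in a patient leaving for another reason.

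A reader might also count physical examination as affected in every case. At Days 8, 15 and 21 a targeted examination is done only if indicated, so there is often no planned value to displace the ET one. It is affected only on the per-visit reading, or where the same body system was examined at the planned visit. Although 5.13.5 says "A shift table will be also presented, with shift from baseline to each post-baseline visit", the listed shift table runs to Day 28 only.

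Finally, 5.2.17 ("Only values collected at scheduled assessments values will be tabulated, unless otherwise stated") might look like a second exclusion. It governs unscheduled and repeat assessments, whereas ET has its own place in the Schedule of Assessments and its own rule in 5.2.4.

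**Conclusion.** The point holds as a cheap, minor improvement. Following 5.2.4 as written leaves withdrawal measurements out of 13 safety tables and the by-timepoint C-SSRS table whenever ET follows a completed Day 8, 15 or 21 visit in the same window. The day counts depend only on Table 3 and the visit tolerance. The share of patients depends on the planning drop-out rate, the assumed spread of exit days and full ET attendance, none of which the documents establish; the alternatives tried give 4.3% to 11.5%.

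It would go too far to say that the plan discards patients' only post-baseline TSH, coagulation and ACTH/cortisol values. That follows only on the per-visit reading, and the clause on incomplete assessments supports the other one. What the text shows is an ambiguity with a real consequence either way. Likewise, 5.13.2 says "A summary of the number of abnormal parameter values will also be provided" without saying whether displaced ET values count.

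The C-SSRS since-baseline outcomes in 5.2.13 span all double-blind treatment and should not be affected. The primary efficacy result is not in question here.

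**What to change.** - **SAP 5.2.4:** apply the exclusion per assessment, so that an ET value is dropped from a visit row only when the same test has a value at that planned visit.
- **SAP 5.13.2–5.13.4 and 5.13.8–5.13.10:** add one row for the last post-baseline value, including ET, with the matching shift for laboratory tests and ECG. Report tests scheduled after baseline only at Day 28 or ET in that row, not under Day 8, 15 or 21. A last-value row is preferable to a worst-value row because it shows the measurement at withdrawal, which is what is missing.
- **SAP 5.13.2:** state that ET values are included in the abnormal-laboratory count (Table 14.3.4).

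Leave 5.2.17, the primary imputation and Sensitivity Analysis #1 unchanged.

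The cost is SAP wording and minor programming on data already collected, and one extra row or shift panel per table. The extrapyramidal tables also need a footnote, because ratings at ET are exempt from the 3-to-6-hour post-dose timing that applies at planned visits.

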5.3 Patient Withdrawal/Discontinuation Criteria

All patients are free to withdraw from participation in this study at any time for any reason and without prejudice.

A patient will be considered to have completed the study when they complete the End of Study (EoS) Visit (Visit 7). If a patient is discontinued at any time after randomization into the study, the Investigator will make every effort to follow the patient and complete the follow-up procedures at an Early Termination (ET) Visit as follows:

- Recording of concomitant medications (e.g., prescription and nonprescription medications)
- Full physical examination
- Bodyweight, BMI (derived programmatically from body weight and height measurements), and waist circumference
- Vital signs
- Resting 12-lead ECG (triplicate, further information in Section 8.2.3)
- Collection of blood and urine samples for clinical laboratory tests. Additional information is presented in the footnotes to the schedule of assessments (SoA) (Table)
- Urine pregnancy test for all females of childbearing potential
- Assessment and recording of AEs
- PANSS, PCRS must be administered before PANSS

CGI-S

Confidential Page 43 of 102

- C-SSRS
- AIMS
- BARS
- SAS
- Cogstate test

Patients may be replaced; however, this must be assessed on a case-by-case basis and be approved by the Sponsor or their designee.

The data on ET will be captured in electronic case report form (eCRF) that should be collected for every patient who receives study drug, whether or not the patient completes the study. The reason for any early discontinuation should be indicated on this form. The primary reason for a patient discontinuing early should be selected from the following standard categories:

- Adverse Event: Clinical or laboratory events occurred that, in the medical judgment of the Investigator for the best interest of the patient, are grounds for discontinuation. These events include SAEs and nonserious AEs regardless of relation to the study drug.
- Lack of Efficacy: Worsening of psychotic symptoms.
- Non-compliance with study drug according to the PI.
- *Protocol Deviation*: The patient's findings or conduct failed to meet the protocol entry criteria or failed to adhere to the protocol requirements (e.g., drug non-compliance, failure to return for defined number of visits).

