- Important note: Free T4 will be measured only if the result for TSH is abnormal.
- 5. Standard 12-lead ECGs (in triplicate) will be performed after the patient has been supine and at rest for ≥5 minutes. The captured ECGs must be separated by at least 1 minute. A central ECG service will be utilized to review all ECGs in order to standardize interpretations for the safety analysis. In addition, ECG results will be evaluated at the investigational site to monitor safety during the trial. Any Screening ECG with abnormal result(s) considered to be clinically significant should be repeated to confirm the finding(s) before excluding the patient from the trial. Patients will be randomized based on Screening ECG results from the central reader and Baseline ECG results from the trial site. If the Baseline ECG results from the central reader, when available, indicate a QTcF >450 msec at Baseline, the Investigator must contact the Medical Monitor to discuss the patient's continued participation in the trial. ECGs scheduled for the same visit as blood samples are to be completed before blood is drawn.
- Vital signs will include body temperature, SBP, DBP, and heart rate. Blood pressure and heart rate will be measured in the following order: supine, sitting and standing after the patient has been in each position for at least 3 minutes. Vital signs scheduled for the same visit as blood sample have to be completed before blood is drawn.

Confidential Page 56 of 102

- The recording of AEs is to start immediately after the ICF is signed and up to 14 days after the end of EoT.
- PK analyses will include the First 60 randomized patients regardless of cohort. PK blood samples will be collected on Day 1, 8, and 21 during the following timepoints after the morning dose: 15 minutes, 30 minutes, 1, 2, 3, 4, 8, and 24 hours. See protocol Section 8.3. On Day 1 only, a pre-dose PK blood sample will be collected. Samples are collected after ECGs and vital signs. The total volume of blood to be collected during the Screening, treatment, and End of Stabilization period is 161 mL. Approximately 21 mL of blood will be collected during the Screening Visit, 130 mL will be collected during the 28-day Treatment Period, and 10 mL will be collected during the End of Stabilization period.
- w. On Day 29 patients are to be started on standard antipsychotic medication as prescribed by the Investigator.

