7.2.11 Stabilization Period (Study Days 29 Through 33)

Patients are to remain inpatient and be restabilized on standard-of-care antipsychotics, which may be started on Day 29. No other assessments are scheduled, and therefore no formal visits are shown in the SoA. However, any AEs observed or reported and concomitant medications may be recorded. If any assessments are required in order to evaluate an AE, an unscheduled visit may be conducted at the discretion of the PI.

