### 5.11.3 Sensitivity Analysis

#### 5.11.3.1 Sensitivity Analysis #1: Re-mapped Early Termination Assessments

The primary analysis will be repeated but including PANNS values obtained during early termination assessments in the analysis, i.e. by re-mapping them to the analysis windows described in Section 5.2.4 in place of PANSS collected at the planned visit mapped to the same analysis window. Similar displays and quantities to the primary analysis will be provided.

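### SAP Table 3 maps early-termination assessments on Days 29 and 30 to Day 28, so a PANSS possibly taken after the switch to a standard antipsychotic can stand as Week 4

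*SAP*

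**What the plan says.** **Mapping.** SAP 5.2.4 states: "Early termination assessments will be mapped to closest scheduled visit using the analysis windows described in Table 3". The Day 28 row of Table 3 runs from Day 25 to Day 30. Assignment is by study day alone.

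**Use of the mapped value.** SAP 5.2.4 gives three rules.
- If the planned visit took place and data were collected, "then the early termination assessment will not be included in the statistical analyses or summaries of any endpoint"; the ET value is listed only.
- If the planned visit did not take place, or took place without all applicable assessments, "then assessments from the early termination visit mapped to that visit will be used in the statistical analyses and summaries".
- For sensitivity analyses of the primary endpoint, where the planned PANSS was correctly completed, "the PANSS score collected at the early termination assessment will be used to replace the primary endpoint value at the planned visit". SAP 5.11.3.1 (Sensitivity Analysis #1) repeats this: ET scores are used "in place of PANSS collected at the planned visit mapped to the same analysis window".

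**Treatment timeline.** Protocol 7.2.10 makes Day 28 the last dosing day. Footnote w of the Schedule of Assessments (Protocol 7.1) says: "On Day 29 patients are to be started on standard antipsychotic medication as prescribed by the Investigator". Protocol 7.2.11 says that patients are to "be restabilized on standard-of-care antipsychotics, which may be started on Day 29". Protocol 6.7 also lifts the limits on lorazepam, benztropine and propranolol in the stabilization period.

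**When an ET visit occurs.** Protocol 5.3 opens the ET procedures with "If a patient is discontinued at any time after randomization into the study" and includes PANSS among them. Protocol 7.2.14 repeats the condition. Under Protocol 5.3 a patient completes the study only at the End of Study visit.

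**Intercurrent events.** SAP 2.3, Table 1, lists prohibited medication and emergency treatment, each before Week 4, both under treatment policy.

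**The concern.** Week 4 is meant to compare LB-102 with placebo at the end of 28 days of dosing. A score from Day 29 or 30 comes after the last randomized dose, when patients in every arm may have begun a standard antipsychotic chosen by the investigator. Nothing in the SAP excludes such a score.

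Two things are at stake. First, Sensitivity Analysis #1 is there to test the primary result, but in this window it can discard the protocol-defined Day 28 measurement for a later one that may be affected by another drug. Second, in the primary analysis an observed Day 29-30 score can pre-empt the imputation that the SAP specifies. The clearest case is a patient who stops for lack of efficacy or a drug-related adverse event late in Week 4, misses Day 28 and has the ET visit on Day 29 or 30. That patient would contribute an observed, possibly post-switch score instead of a value from the worst-score MNAR step.

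**Working it through.** **1. Day numbering.** SAP 5.2.5 counts the first dose as Day 1. SAP Day 29 is therefore protocol Day 29, with no one-day offset.

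**2. Reproducing Table 3.** Take midpoints between scheduled days 8, 15, 21, 28 and 33 (the end-of-stabilization visit), rounding down and giving ties to the earlier visit:
- (8 + 15)/2 = 11.5, window ends Day 11
- (15 + 21)/2 = 18.0, window ends Day 18
- (21 + 28)/2 = 24.5, window ends Day 24
- (28 + 33)/2 = 30.5, window ends Day 30

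All four match Table 3. Using Day 33 for the last midpoint is an inference; the SAP does not say how Day 30 was chosen. If the inference is right, Day 30 comes from an ordinary convention that takes no account of the change of treatment between Days 28 and 29.

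**3. Share of the window after the last dose.** Days 25 to 30 are 30 - 25 + 1 = 6 days. Days 29 and 30 follow the last dose: 2/6 = 33% of the window. The schedule gives Days 8, 15 and 21 a tolerance of one day either side and gives Day 28 none, so the extension beyond Day 28 comes from the SAP alone.

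**4. What happens to an ET PANSS taken on Day 29 or 30.**

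| Day 28 visit | Primary analysis | Sensitivity Analysis #1 |
|---|---|---|
| PANSS correctly completed, visit complete | Day 28 score kept; ET score listed | ET score replaces Day 28 score |
| Visit missed | ET score becomes Week 4 | ET score becomes Week 4 |
| PANSS done, another assessment missing | Not clear from the wording | ET score replaces Day 28 score |

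In the second row, imputation is bypassed. The sample code in SAP 5.11.2 assigns the worst-score value only where Week 4 is missing, and the MAR step likewise fills only missing values.

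**5. Coverage by the estimand.** The listed events must occur before Week 4. The Day 29 start of a standard antipsychotic is directed by the protocol and follows Day 28, so it is neither of them.

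**6. Scale, on assumed inputs only.** Suppose a fraction f of an arm's Week 4 values comes from Days 29-30 and is shifted by s points. The arm mean then moves by about f × s. The documents give neither quantity.
- f = 1%, s = 3: 0.01 × 3 = 0.03 point; 0.03/8 = 0.4% of the planned 8-point difference
- f = 5%, s = 10: 0.05 × 10 = 0.5 point; 0.5/8 = 6.25%
- f = 10%, s = 10: 0.10 × 10 = 1.0 point; 1.0/8 = 12.5%

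These are movements of one arm's mean. The bias in the comparison is the difference between the two arms' movements. If f = 5% and s = 10 in both arms, the net is 0.5 - 0.5 = 0.

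**The case against.** The strongest reply is that an ET visit after Day 28 goes against the schedule. The Schedule of Assessments has one shared column for Day 28 and ET. Protocol 7.2.10 applies the Day 28 assessments to patients who discontinue before that visit. Protocol 5.3 ties completion-type evaluations to stopping dosing early, and Protocol 7.2.11 plans no such assessments for Days 29 to 33. This stands as an argument that cases will be few. It does not remove the rule: Protocol 5.3 and 7.2.14 set no upper limit on when a discontinuation leads to an ET visit, no deadline for the visit is stated, and Table 3 itself provides for Days 29 and 30.

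Second, a Day 29 PANSS may precede the first antipsychotic dose. It may also fall about one dosing interval after the last study dose: Protocol Table 14.1 gives mean half-lives of about 12 to 14 hours, and Protocol 7.2.12 expects minimal plasma levels only within 5 days of the end of treatment. This stands. Exposure to the new drug is possible, not certain, and a pre-switch Day 29 score is a reasonable stand-in for a missed Day 28. The remedy should keep it.

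Third, treatment policy retains scores after other antipsychotics by design. That is correct before Week 4, and SAP 2.3 and Protocol 10.4.4.2 both say so. A reader might infer that every ET score taken after an antipsychotic should be dropped. The documents do not support that: it would discard data that the primary estimand keeps. The problem is specific to Days 29 and 30.

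**Conclusion.** The point holds within limits. As written, a Day 29-30 ET PANSS replaces a correctly completed Day 28 PANSS in Sensitivity Analysis #1. It also supplies the Week 4 value in the primary analysis when the Day 28 visit was missed, and possibly when it was only partly completed. No intercurrent-event rule covers it.

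Three stronger readings are not supported.
- *A valid Day 28 score is overwritten in the primary analysis.* With a complete Day 28 visit the ET value is only listed; replacement is confined to sensitivity analysis.
- *Scales other than PANSS are overwritten too.* The replacement rule names PANSS only. For CGI-S, movement scales, laboratory values, ECG and weight, a Day 29-30 value enters only when Day 28 was missed or incomplete.
- *The result is diluted by a known amount.* If both arms switch, convergence is plausible. But the 0.03 to 1.0 point range rests on assumed fractions and shifts, and its upper end assumes a 10-point change within two days, more than the 8-point difference planned over four weeks. Neither the size nor the direction of a net bias is established.

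The number of patients is not given and is probably small. This is a targeted correction to a mapping rule, not a threat to the design. Sample size, alpha and the Hochberg thresholds do not change.

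**What to change.** Add to SAP 5.2.4, before database lock and unblinding:

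> An ET assessment on Day 29 or 30 never replaces a completed Day 28 assessment, including in Sensitivity Analysis #1. If the Day 28 assessment is missing, a Day 29-30 ET assessment is mapped to Day 28 only if it was made before the first dose of a standard antipsychotic started on or after Day 29; otherwise it is listed only, and the Week 4 PANSS is handled as missing under Section 5.11.2. ET assessments up to Day 28 are mapped as now, whatever medication was taken, in line with the treatment-policy estimand.

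This also settles the partly completed Day 28 visit for Day 29-30 ET values, because it works assessment by assessment. If the ET assessment and the first antipsychotic dose share a date and no times are recorded, the SAP should say which way the value falls; treating it as post-switch is the cautious choice.

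Footnote w and Protocol 7.2.11 differ on whether the Day 29 start is directed or permitted, and they should be reconciled. The added text works under either, since it depends on the actual first dose.

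Cost: one short paragraph and a programming check against the concomitant-medication data that Protocol 6.7 already requires in the eCRF. The downside is that a few ET values move from the summaries to the listings, and for PANSS total score those patients' Week 4 values are imputed.
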